7. STUDY CALENDAR

Baseline evaluations are to be conducted within 1 week prior to administration of protocol therapy. Scans and x-rays must be done within 4 weeks prior to the start of therapy. For subsequent weeks, the studies may be performed within \pm 2 days of the indicated dates.

	Pre-Study	Wk 1	Wk 2	Wk 3	Wk 4	Wk 5	Wk 6	Wk 7	Wk 8	Wk 9	Wk 10	Wk 11	Wk 12+ ^g	Off Study
VORINOSTAT ^{a, g}		X	X		X	X		X	X		X	X		
Rituximab		X			X			X			X			
Lovenox		X	X	X	X	X	X	X	X	X	X	X	X	
Informed consent	X													
Demographics	X													
Medical history	X													
Height	X													
B-HCG ^b	X													
Record concurrent medications	X	X-----X												
Physical exam	X	X			X			X			X			X
Vital signs	X	X			X			X			X			X
Weight	X	X			X			X			X			X
Performance status	X	X			X			X			X			X
CBC w/diff, plts	X	X			X			X			X			X
Serum chemistry ^c	X	X			X			X			X			X
Correlatives ⁱ	X		X											
Adverse event evaluation		X-----X												X
Tumor measurements	X	Tumor measurements are repeated every 3 cycles (~9 weeks) ^j . Bone marrow assessment should be done within 4 weeks of starting therapy, and repeated every 3 cycles if the initial marrow shows involvement by lymphoma. Documentation (radiologic) must be provided for patients removed from study for progressive disease.												X ^d
Radiologic evaluation	X	CT scans are repeated every 3 cycles (~9 weeks) ^j . Follow up PET scans for patients with PET positive disease is optional, but suggested.												X ^d
Bone marrow	X ^h									X				

- a: VORINOSTAT: Starting dose 200mg orally twice daily for 2 weeks, followed by 1 week of rest (21 day cycle).
- b: Serum pregnancy test (women of childbearing potential).
- c: Albumin, alkaline phosphatase, total bilirubin, bicarbonate, BUN, calcium, chloride, creatinine, glucose, LDH, phosphorus, potassium, total protein, SGOT [AST], SGPT [ALT], sodium.
- d: Off-study evaluation.
- g. Patients with partial response or stable disease may continue to receive VORINOSTAT until progression. Patients who achieve CR will receive two further cycles of VORINOSTAT and then discontinue drug. Follow up radiological studies will continue every three months for one year, then every six months for the next two years.
- h. Bone Marrow aspiration and biopsy may be performed up to four weeks prior to starting study drug, and if positive should be repeated every three cycles.
- i. For details see section 11.
- j. After one year of treatment, if the patient achieved two consecutive PR based on prior CT scans or PET, the radiological assessment can be done after every 4 cycles instead of 3 cycles. If patients achieved CR, follow up radiological studies will continue every 3 months for one year, then every six months for the next two years.

8. MEASUREMENT OF EFFECT

For the purposes of this study, patients should be reevaluated for response every three cycles (~ 9 weeks) by radiological and marrow studies as described in the study calendar (section 8). After one year of treatment, if the patient achieved two consecutive PR based on prior CT scans or PET, the radiological assessment can be done after every 4 cycles instead of 3 cycles. If patients achieved CR, follow up radiological studies will continue every 3 months for one year, then every six months for the next two years.

8.1 Response Criteria

(as per
Cheson BD, et
al. J Clin
Oncol. 2007
Feb
10;25(5):579-
86.)Response

Definition Nodal Masses Spleen, Liver Bone Marrow

CR	Disappearance of all evidence of disease	(a) FDG-avid or PET positive prior to therapy; mass of any size permitted if PET negative (b) Variably FDG-avid or PET negative; regression to normal size on CT	Not palpable, nodules disappeared	Infiltrate cleared on repeat biopsy; if indeterminate by morphology, immunohistochemistry should be negative
PR	Regression of measurable disease and no new sites	≥50% decrease in SPD of up to 6 largest dominant masses; no increase in size of other nodes (a) FDG-avid or PET positive prior to therapy; one or more PET positive at previously involved site (b) Variably FDG-avid or PET negative; regression on CT	≥50% decrease in SPD of nodules (for single nodule in greatest transverse diameter); no increase in size of liver or spleen	Irrelevant if positive prior to therapy; cell type should be specified
SD	Failure to attain CR/PR or PD	(a) FDG-avid or PET positive prior to therapy; PET positive at prior sites of disease and no new sites on CT or PET (b) Variably FDG-avid or PET		

Abbreviations: CR, complete remission; FDG, [¹⁸F]fluorodeoxyglucose; PET, positron emission tomography; CT, computed tomography; PR, partial remission; SPD, sum of the product of the diameters; SD, stable disease; PD, progressive disease.

CR:

1. Complete disappearance of all detectable clinical evidence of disease and disease-related symptoms if present before

therapy.

2a. Typically FDG-avid lymphoma: in patients with no pretreatment PET scan or when the PET scan was positive before therapy, a post-treatment residual mass of any size is permitted as long as it is PET negative.

2b. Variably FDG-avid lymphomas/FDG avidity unknown: in patients without a pretreatment PET scan, or if a pretreatment PET scan was negative, all lymph nodes and nodal masses must have regressed on CT to normal size (≤ 1.5 cm in their greatest transverse diameter for nodes > 1.5 cm before therapy). Previously involved nodes that were 1.1 to 1.5 cm in their long axis and more than 1.0 cm in their short axis before treatment must have decreased to ≤ 1.0 cm in their short axis after treatment.

3. The spleen and/or liver, if considered enlarged before therapy on the basis of a physical examination or CT scan, should not be palpable on physical examination and should be considered normal size by imaging studies, and nodules related to lymphoma should disappear. However, determination of splenic involvement is not always reliable because a spleen considered normal in size may still contain lymphoma, whereas an enlarged spleen may reflect variations in anatomy, blood volume, the use of hematopoietic growth factors, or causes other than lymphoma.

4. If the bone marrow was involved by lymphoma before treatment, the infiltrate must have cleared on repeat bone marrow biopsy. The biopsy sample on which this determination is made must be adequate (with a goal of > 20 mm unilateral core). If the sample is indeterminate by morphology, it should be negative by immunohistochemistry. A sample that is negative by immunohistochemistry but that demonstrates a small population of clonal lymphocytes by flow cytometry will be considered a CR until data become available demonstrating a clear difference in patient outcome.

Cru

The use of the above definition for CR and that below for PR eliminates the category of CRu.

PR

The designation of PR requires all of the following:

1. At least a 50% decrease in sum of the product of the diameters (SPD) of up to six of the largest dominant nodes or nodal masses. These nodes or masses should be selected according to all of the following: they should be clearly measurable in at least 2 perpendicular dimensions; if possible they should be from disparate regions of the body; and they should include mediastinal and retroperitoneal areas of disease whenever these sites are involved.
2. No increase should be observed in the size of other nodes, liver, or spleen.
3. Splenic and hepatic nodules must regress by $\geq 50\%$ in their SPD or, for single nodules, in the greatest transverse diameter.
4. With the exception of splenic and hepatic nodules, involvement of other organs is usually assessable and no measurable disease should be present.
5. Bone marrow assessment is irrelevant for determination of a PR if the sample was positive before treatment. However, if positive, the cell type should be specified (eg, large-cell lymphoma or small neoplastic B cells). Patients who achieve a CR by the above criteria, but who have persistent morphologic bone marrow involvement will be considered partial responders.
When the bone marrow was involved before therapy and a clinical CR was achieved, but with no bone marrow assessment after treatment, patients should be considered partial responders.
6. No new sites of disease should be observed.

7. Typically FDG-avid lymphoma: for patients with no pretreatment PET scan or if the PET scan was positive before therapy, the post-treatment PET should be positive in at least one previously involved site.
8. Variably FDG-avid lymphomas/FDG-avidity unknown: for patients without a pretreatment PET scan, or if a pretreatment PET scan was negative, CT criteria should be used.

In patients with follicular lymphoma or mantle-cell lymphoma, a PET scan is only indicated with one or at most two residual masses that have regressed by more than 50% on CT; those with more than two residual lesions are unlikely to be PET negative and should be considered partial responders.

Stable Disease

Stable disease (SD) is defined as the following:

1. A patient is considered to have SD when he or she fails to attain the criteria needed for a CR or PR, but does not fulfill those for progressive disease (see Relapsed Disease [after CR]/Progressive Disease [after PR, SD]).
2. Typically FDG-avid lymphomas: the PET should be positive at prior sites of disease with no new areas of involvement on the post-treatment CT or PET.
3. Variably FDG-avid lymphomas/FDG-avidity unknown: for patients without a pretreatment PET scan or if the pretreatment PET was negative, there must be no change in the size of the previous lesions on the post-treatment CT scan.

Relapsed Disease (after CR)/Progressive Disease (after PR, SD)

Lymph nodes should be considered abnormal if the long axis is more than 1.5 cm regardless of the short axis. If a lymph node has a long axis of 1.1 to 1.5 cm, it should only be considered abnormal if its short axis is more than 1.0. Lymph nodes $\leq 1.0 \times \leq 1.0$ cm will not be considered as abnormal for relapse or progressive disease.

1. Appearance of any new lesion more than 1.5 cm in any axis during or at the end of therapy, even if other lesions are decreasing in size. Increased FDG uptake in a previously unaffected site should only be considered relapsed or progressive disease after confirmation with other modalities. In patients with no prior history of pulmonary lymphoma, new lung nodules identified by CT are mostly benign. Thus, a therapeutic decision should not be made solely on the basis of the PET without histologic confirmation.
2. At least a 50% increase from nadir in the SPD of any previously involved nodes, or in a single involved node, or the size of other lesions (eg, splenic or hepatic nodules). To be considered progressive disease, a lymph node with a diameter of the short axis of less than 1.0 cm must increase by $\geq 50\%$ and to a size of 1.5 x 1.5 cm or more than 1.5 cm in the long axis.
3. At least a 50% increase in the longest diameter of any single previously identified node more than 1 cm in its short axis.
4. Lesions should be PET positive if observed in a typical FDG-avid lymphoma or the lesion was PET positive before therapy unless the lesion is too small to be detected with current PET systems (< 1.5 cm in its long axis by CT).

Measurable extranodal disease should be assessed in a manner similar to that for nodal disease. For these recommendations, the spleen is considered nodal disease. Disease that is only assessable (eg, pleural effusions, bone lesions) will be recorded as present or absent only, unless, while an abnormality is still noted by imaging studies or physical examination, it is found to be histologically negative.

9. REGULATORY AND REPORTING REQUIREMENTS

The descriptions and grading scales found in the revised NCI Common Terminology Criteria for Adverse Events (CTCAE) version 3.0 will be utilized for adverse event reporting. All appropriate treatment areas should have access to a copy of the CTCAE version 3.0. A list of adverse events that have occurred or might occur (Comprehensive Adverse Events and Potential Risks list) can be found in Section 6 (Pharmaceutical Information). *A copy of the CTCAE version 3.0 can be downloaded from the CTEP web site (<http://ctep.cancer.gov/reporting/ctc.html>).*

9.1 Expedited Adverse Event Reporting

We agree to provide Merck (Attn: Worldwide Product Safety; [contact]) with copies of all serious adverse experiences within two working days. Additionally, we agree to report any pregnancy occurring in association with use of a Merck Product to Merck (Attn: Worldwide Product Safety; [contact]). A copy of all 15 Day Reports and Annual Progress Reports is submitted as required by FDA, European Union (EU), Pharmaceutical and Medical Devices agency (PMDA) or other local regulators by the investigator. We agree to cross reference this submission according to local regulations, to the Merck Investigational Compound number (IND, CSA, etc) at the time of submission. Additionally we agree to submit a copy of these reports to Merck (Attn: Worldwide Product Safety; [contact]) at the time of submission to the appropriate regulatory agency.

Notes:

* In studies involving human subjects, serious adverse experience means any experience that suggest a significant hazard, contraindication, side effect or precaution. A serious adverse experience includes any experience that is fatal or immediately life threatening, results in a persistent or significant disability/incapacity, requires or prolongs in-patient hospitalization, or is a congenital anomaly, cancer, or overdose.

Other important medical events that may not result in death, not be life-threatening, or not require hospitalization may be considered a serious adverse experience when, based upon appropriate medical judgment, the event may jeopardize the subject/patient and may require medical or surgical intervention to prevent one of the outcomes listed previously.

9.1.2 Expedited Adverse Event Reporting Exclusions

None

9.2 Registration Guidelines

Once the signed informed consent has been obtained and all pretreatment evaluations have been performed, patients will be entered on study. To register a patient, the research nurse or data manager must complete the Eligibility Checklist and FAX a copy of this and the informed consent including the Bill of Rights to the Coordinator at the City of Hope ([contact]). The research nurse or data manager will call the Coordinator at [name], and after verifying the eligibility, the Coordinator will register the patient onto the study and assign a patient accession number

Protocol waivers and/or treatment deviations are not allowed other than in the case of delay as described in sections 5.1 and 5.2.

9.3 COH DSMB Data Reporting

A) Definition of Risk Level

This is a Risk Level 3 study, as defined in the “City of Hope Data and Safety Monitoring Plan”, <http://www.coh.org/dsmc/Pages/forms-and-procedures.aspx> because it is a Phase 2 clinical trial where the risks are at least balanced by the potential benefit to subjects and the importance of the knowledge that may result.

B) Monitoring and Personnel Responsible for Monitoring

The Protocol Management Team (PMT) consisting of the PI, Collaborating Investigator, CRA, protocol nurse, and statistician is responsible for monitoring the data and safety of this study, including implementation of any stopping rules for safety and efficacy.

Table 1: City of Hope PMT Reporting Timelines for the DSMC

Risk Level	Phase	Standard Reporting Requirement
RL 1, RL2, and Compassionate Use Studies	No reports required	
3	I	Every 3 months from activation date, as indicated in MIDAS
3	Pilot, Feasibility, II-IV	Every 6 months from activation date, as indicated in MIDAS
4	Pilot, Feasibility, I-IV	Every 3 months from activation date, as indicated in MIDAS

Data and safety will be reported to the COH DSMC using the PMT report and submitted according to the timelines in Table 1 above. Protocol specific data collection will include the following items: hematologic response and toxicities of treatment.

C) Definitions

Adverse event (AE) - An adverse event is any untoward medical experience or change of an existing condition that occurs during or after treatment, whether or not it is considered to be related to the protocol intervention.

Unexpected Adverse Event [21 CFR 312.32 (a)] – An adverse event is unexpected if it is not listed in the investigator’s brochure and/or package insert; is not listed at the specificity or severity that has been observed; is not consistent with the risk information described in the protocol and/or consent; is not an expected natural progression of any underlying disease, disorder, condition, or predisposed risk factor of the research participant experiencing the adverse event.

Expected Adverse Event - Any event that does not meet the criteria for an unexpected event OR is an expected natural progression of any underlying disease, disorder, condition, or predisposed risk factor of the research participant experiencing the adverse event

Serious Adverse Event (SAE) [21 CFR 312.32] is defined as *any expected or unexpected adverse event* that results in any of the following outcomes:

- Death
- Is life-threatening experience (places the subject at immediate risk of death from the event as it occurred)
- Unplanned hospitalization (equal to or greater than 24 hours) or prolongation of existing hospitalization
- A persistent or significant disability/incapacity
- A congenital anomaly/birth defect
- Secondary Malignancy
- Any other adverse event that, based upon appropriate medical judgment, may jeopardize the subject’s health and may require medical or surgical intervention to prevent one of the outcomes listed above (examples of such events include allergic bronchospasm requiring intensive treatment in the emergency room or at home, blood dyscrasias or convulsions that do not result in inpatient hospitalization, or the development of drug dependency or drug abuse).

Unanticipated problem (UP) – Any incident, experience, or outcome that **meets all three** of the following criteria:

1. Unexpected (in term nature, severity, or frequency) given the following: a) the research procedures described in the protocol-related documents such as the IRB approved research protocol, informed consent document or Investigator Brochure (IB); and b) the characteristics of the subject population being studied; **AND**
2. Related or possibly related to participation in the research (possibly related means there is a reasonable possibility that the incident, experience, or outcomes may have been caused by the drugs, devices or procedures involved in the research); **AND**
3. Suggests that the research places subjects or others at greater risk of harm (including physical, psychological, economic, or social harm) than previously known or recognized.

D. Reporting of Unanticipated Problems and Adverse Events

Unanticipated Problems: Most unanticipated problems must be reported to the COH DSMC and IRB **within 5 calendar days** according to definitions and guidelines at

<http://www.coh.org/hrpp/Pages/hrpp-policies.aspx>. Any unanticipated problem that occurs during the study conduct will be reported to the DSMC and IRB by submitting electronically in iRIS (<http://iris.coh.org>).

Serious Adverse Events - All SAEs occurring during this study, whether observed by the physician, nurse, or reported by the patient, will be reported according to definitions and guidelines at <http://www.coh.org/hrpp/Pages/hrpp-policies.aspx> and Table 2 below. Those SAEs that require expedited reporting will be submitted electronically in iRIS (<http://iris.coh.org>).

Adverse Events - Adverse events will be monitored by the PMT. Adverse events that do not meet the criteria of serious OR are not unanticipated problems will be reported only in the protocol continuation reports and PMT report (see Table 2 below).

Table 2: City of Hope Adverse Event and Unanticipated Problem Reporting Timelines for the DSMC and IRB

Required Reporting Timelines to DSMC for AE/SAEs
Investigator Initiated Studies

Required Reporting Timeframe to DSMC		
Attribution	UNEXPECTED	EXPECTED
	Death while on active treatment or within 30 days of last day of treatment	
Possibly, Probably, Definitely	5 calendar days	
Unlikely, Unrelated		
	Death after 30 days of last active treatment/therapy	
Possibly, Probably, Definitely	5 calendar days	No reporting required
Unlikely, Unrelated	No reporting required	No reporting required
	Grades 3 and 4 AND meeting the definition of "serious"	
Possibly, Probably, Definitely	5 calendar days	10 calendar days
Unlikely, Unrelated	5 calendar days	10 calendar days
	Grades 1 and 2 AND resulting in "hospitalization"	
Possibly, Probably, Definitely	5 calendar days	10 calendar days
Unlikely, Unrelated	10 calendar days	10 calendar days

Externally Sponsored Studies

Required Reporting Timeframe to DSMC		
Attribution	UNEXPECTED¹	EXPECTED
	Death while on active treatment or within 30 days of last day of treatment	
Possibly, Probably, Definitely	No DSMC reporting required - IRB reporting may be necessary	
Unlikely, Unrelated		
	Death after 30 days of last active treatment/therapy	
Possibly, Probably, Definitely	No DSMC reporting required - IRB reporting may be necessary	
Unlikely, Unrelated		
	Grades 3 and 4 AND meeting the definition of "serious"	
Possibly, Probably, Definitely	No DSMC reporting required - IRB reporting may be necessary	
Unlikely, Unrelated		
	Grades 1 and 2	
Possibly, Probably, Definitely	No DSMC reporting required - IRB reporting may be necessary	

An event determined by the IRB of record to be an Unanticipated Problem (UP) will be communicated to the Investigator and COH DSMC through the COH IRB Operations Director. The DSMC will review the case and make a determination as to whether the study will be suspended, terminated, amended, or allowed to continue without amendment.

Required Reporting Timeframe to IRB of Record		
Attribution	UNEXPECTED	EXPECTED
	Death	
Possibly, Probably, Definitely	5 calendar days	Annual
Unlikely, Unrelated	Annual	Annual
	Grades 3 and 4 AND meeting the definition of a UP	
Possibly, Probably, Definitely	5 calendar days	Annual
Unlikely, Unrelated	Annual	Annual
	Grade 1 and 2 AND meeting the definition of a UP	
Possibly, Probably, Definitely	5 calendar days	Annual
Unlikely, Unrelated	Annual	Annual

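### Section 9.3 D gives two incompatible reporting rules for serious adverse events that are not unanticipated problems: periodic reports only, or the 5- and 10-day timelines of Table 2

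*Combined protocol and SAP*

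**What the plan says.** Section 9.3 D has consecutive paragraphs on unanticipated problems, SAEs and adverse events.

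- **SAE paragraph.** "All SAEs occurring during this study, whether observed by the physician, nurse, or reported by the patient" are to follow institutional policy and Table 2. Section 9.3 C defines an SAE as "any expected or unexpected adverse event" with a listed outcome, so expected events are included.
- **Adverse Events paragraph.** "Adverse events that do not meet the criteria of serious OR are not unanticipated problems will be reported only in the protocol continuation reports". The sentence names the PMT report as a second destination and points the reader to Table 2.
- **Unanticipated problem (Section 9.3 C).** Three criteria must all be met. The first begins "Unexpected (in term nature, severity, or frequency) given the following"; the second is "Related or possibly related to participation in the research"; the third is that the event suggests greater risk than was previously known.
- **Periodic reporting (Section 9.3 B, Table 1).** For a Risk Level 3, Phase II study the PMT report goes to the DSMC "Every 6 months from activation date, as indicated in MIDAS".
- **Expedited reporting (Table 2, investigator-initiated DSMC block).** Timelines are 5 or 10 calendar days for most serious events, whether or not the event is an unanticipated problem.

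On efficacy content, Section 9.3 B says: "Protocol specific data collection will include the following items: hematologic response and toxicities of treatment".

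**The concern.** The sentence on adverse events was presumably meant for events that need no expedited report. Joined by OR, its two conditions reach much further: failing either one is enough to send an event to periodic reports only. An SAE that is not an unanticipated problem fails the second condition. The SAE paragraph puts the same event under Table 2, and no rule of precedence is given. Section 10.1 does not help, because it refers the reader to section 10 for adverse event reporting, which is the statistics section itself.

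At stake is how soon the DSMC hears of these SAEs. The other early routes do not reach it: Section 9.1 sends SAEs to the drug supplier within two working days, and the Appendix D form goes to the consortium coordinator within 24 hours of onset.

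A smaller matter in the same section is that the efficacy item named for data collection is not one the trial defines.

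**Working it through.** No power or error-rate figure is involved. The check is to route each serious-event cell of Table 2 under the printed rule and compare the result with the timeline in that cell.

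**Inputs.** Timelines in calendar days from the investigator-initiated DSMC block of Table 2: 4 event classes × 2 attributions × 2 levels of expectedness = 16 cells. Related means possibly, probably or definitely; unrelated includes unlikely.

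| Event class | Unexpected, related | Expected, related | Unexpected, unrelated | Expected, unrelated |
|---|---|---|---|---|
| Death on treatment or within 30 days | 5 | 5* | 5* | 5* |
| Death after 30 days | 5 | none | none | none |
| Grade 3–4 and serious | 5 | 10 | 5 | 10 |
| Grade 1–2 with hospitalization | 5 | 10 | 10 | 10 |

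*One value is shown for this block; it is read here as a merged cell.

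**Printed rule.** Periodic only if (not serious) OR (not an unanticipated problem). All 16 cells are treated as serious, so the rule reduces to: periodic only if not an unanticipated problem. Such a problem must be both unexpected and related, so the three right-hand columns go to periodic reports only.

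- Cells routed to periodic reports only: 4 × 3 = 12.
- Of these, cells with a Table 2 timeline: 3 + 0 + 3 + 3 = 9. Four carry 5 days (three early-death cells and one grade 3–4 cell); five carry 10 days.
- Cells with no conflict: 12 − 9 = 3, all deaths after 30 days.
- Expected cells alone (8): four at 10 days, two at 5 days, two with no report required.

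**Sensitivity.**

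- If the early-death value is not a merged cell and applies only where it is printed, the conflicts fall to 9 − 3 = 6.
- The left-hand column was counted as free of conflict because those events can be unanticipated problems. If such an event does not meet the third criterion, it too goes to periodic reports only. All four of those cells carry 5 days, so the upper count is 9 + 4 = 13.

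**Rule with AND.** Periodic only if (not serious) AND (not an unanticipated problem). No serious event satisfies the first part, so 0 of 16 cells are routed to periodic reports and there are 0 conflicts.

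**Longest wait.** Half a year is 365.25 / 2 = 182.6 days. Against the table, notice could be late by up to 182.6 − 10 = 172.6 days or 182.6 − 5 = 177.6 days. An event shortly before a PMT report would wait far less.

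**Efficacy item.** Section 8.1 defines CR and PR by nodal masses, spleen and liver, and marrow. The Section 10.1 rule counts CR+PR: 4 or more of 17 to continue, 10 or more of 33 at the end. Neither section defines a hematologic response.

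**The case against.** The strongest reply is that the plan, read as a whole, points to expedited reporting. The SAE paragraph comes first, is specific and covers all SAEs. The disputed sentence stands under a different label and itself points to Table 2. That is two statements and a table against one conjunction. This much stands. A reader might infer that the plan requires expected SAEs to wait six months; the documents do not support that. They contradict themselves, and late notice follows only if a site lets the Adverse Events sentence override the SAE paragraph.

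A second reply is that the two limbs match two recipients. The DSMC rows turn largely on seriousness or hospitalization. The non-death IRB rows turn on meeting the definition of an unanticipated problem, with expected events reported annually. This would reconcile the rules, but the sentence does not assign either limb to a recipient and says such events go only to periodic reports.

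Other inferences also go too far:

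- **Ten days for every expected SAE.** This does not hold for deaths: 5 days on treatment or within 30 days (on the merged-cell reading), and no DSMC report for later expected deaths.
- **Eighteen patients exposed during the delay** (3 a month × 6 months). This combines the longest wait with full accrual; it is not an expected effect.
- **The five thromboembolic events as proof of harm.** Section 4.3.8 describes them as asymptomatic CT findings. The documents do not show that they were SAEs or that a report was delayed.
- **DSMC reports without the responder count.** The list in 9.3 B says what data collection will include and is not exclusive. The PMT includes the statistician and implements any stopping rules, and the Section 10.1 rule does not depend on the phrase.

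**Conclusion.** The contradiction is real and should be corrected. Read literally, one sentence in Section 9.3 D removes from expedited DSMC reporting a set of SAEs that the adjoining paragraph and Table 2 place there: 9 of the 12 affected cells, or 6 of 12 if the early-death entry is not merged. It affects unexpected but unrelated SAEs as well as expected ones. The consequence is possible delay, at most to the next six-monthly PMT report. Design, sample size and analysis are untouched.

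This rests on two assumptions. First, the investigator-initiated block applies. The text available does not say so, although Section 9.1 has the investigator submitting regulatory reports with copies to the supplier. The externally sponsored block requires no DSMC reporting, so the conflict with DSMC timelines would then disappear. Second, expected has the same meaning in Table 2 and in the definition of an unanticipated problem. That definition also allows an event to be unexpected in frequency, so a listed event occurring unusually often could still qualify.

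The hematologic response wording is a minor terminology error.

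**What to change.** - In the Adverse Events paragraph of Section 9.3 D, limit the periodic-only rule to events that are *not serious AND not unanticipated problems*. Table 2 then governs all SAEs and agrees with the SAE paragraph.
- In Section 9.3 B, replace hematologic response with CR+PR per Section 8.1, the endpoint used in the Section 10.1 rule.

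The cost is one changed conjunction and one replaced term, with a matching edit to the PMT report form if it uses the same term.
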